7.2 Azacitidine

Azacitidine is to be administered in accordance with the terms of its marketing authorization and/or in accordance with local standards of care. Please refer to the approved Prescribing Information for detailed information on how to prepare and administer azacitidine.

7.2.1 Azacitidine Labeling, Packaging, and Supply

Where applicable, each site will procure a supply of azacitidine, which is commercially available.

All study medications must be kept in a secure place under appropriate storage conditions. Refer to the approved Prescribing Information for azacitidine storage conditions. The expiration date on the label must not be exceeded.

The Sponsor or its representatives must be granted access on reasonable request to check drug storage, dispensing procedures, and accountability records.

7.2.2 Preparation and Administration of Azacitidine

Azacitidine is to be prepared and administered in accordance with the terms of its marketing authorization or in accordance with local standards of care. For those sites unable to administer azacitidine according to the recommended administration schedule (for 7 consecutive days), a 5-2-2 administration scheme (5 consecutive days, 2 rest days, and the first 2 days of the following week) is acceptable. Azacitidine should be administered at approximately the same time each day. Each Investigator will declare preference as to which schedule is preferred for a subject and use that schedule throughout the study for this subject.

7.2.3 Precautions and Risks Associated with Azacitidine

Common risks associated with azacitidine administration	
Anemia, neutropenia, and thrombocytopenia	Perform CBCs prior to each treatment cycle and as needed to monitor response and toxicity.
Hepatotoxicity	Use with caution in subjects with severe preexisting liver impairment.
Renal abnormalities	Monitor subjects with renal impairment for toxicity since azacitidine and its metabolites are primarily excreted by the kidneys.

Monitor liver chemistries and serum creatinine prior to initiation of therapy and with each cycle.

Please refer to the approved Prescribing Information for detailed information on the risks associated with the use of azacitidine.

8 CONCOMITANT MEDICATIONS

Concomitant medications will be recorded from the first study drug administration until 30 days after the last study drug administration, or until new treatment for MDS is started.

8.1 Permitted Concomitant Medications

Premedication with antiemetics is allowed according to standard practice guidelines and/or local standards of care.

Prophylaxis with quinolone antibiotics is permitted per local standards of care.

Caution should be taken in concomitant administration of the following:

- Fibrinolysis inhibitors
- Anticoagulant and antiplatelet drugs

Other medications considered necessary for subject safety and well-being may be given at the discretion of the Investigator with the exception of those listed in Section 8.2.

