7.1.4 Precautions and Risks Associated with the Study Drug

Precautions and associated risks with pracinostat	
Hematologic	Treatment with pracinostat has been associated with cytopenias including anemia, thrombocytopenia, and neutropenia. The incidence of cytopenias may increase with increasing doses of pracinostat. Subjects participating in clinical studies of pracinostat should be monitored closely for adverse hematologic affects. The effect of dose reduction on the amelioration of cytopenias has not been established, however prudent clinical management, including supportive care (appropriate use of transfusions and/or hematopoietic growth factors) and dose modification or discontinuation should be followed (see Section 6.5).
Gastrointestinal	Gastrointestinal disturbances (including nausea, vomiting, and diarrhea) have been reported in subjects treated with pracinostat. Standard antiemetic and antidiarrheal medications and appropriate supportive care should be used per normal clinical practice in subjects participating in clinical studies of pracinostat. Preexisting nausea, vomiting, and diarrhea should be adequately controlled before beginning therapy.
QTc Prolongation/Cardiac	Asymptomatic QTc interval prolongation has been observed during clinical studies of pracinostat. Subjects with a CTCAE Grade 2 prolonged QTc interval during screening will not be permitted to participate in clinical studies of pracinostat. Hypokalemia or hypomagnesemia should be corrected prior to pracinostat administration and consideration should be given to monitoring potassium and magnesium in symptomatic subjects (e.g., subjects with nausea, vomiting, diarrhea, fluid imbalance, or cardiac symptoms). See the Investigator's Brochure for additional information on QTc prolongation. Concomitant medications with a known risk of prolonging the QT interval and/or causing Torsades de Pointes are prohibited. In addition, caution should be taken when using concomitant medications with a possible or conditional risk of prolonging the QT interval and/or causing Torsades de Pointes; medications with a possible or conditional risk may be used at the discretion of the Investigator (Appendix H).

Precautions and associated risks with pracinostat	

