8.2 Prohibited Concomitant Medications

The following treatments are prohibited while in this study:

- No other investigational therapy should be given to subjects.
- No anticancer agents should be administered to subjects. If such agents are required, the subject must first be withdrawn from the study.
- HDAC inhibitors (Zolinza [vorinostat], Istodax [romidepsin/depsipeptide]) or valproic acid (which has significant action as a HDAC inhibitor).

- Medications with a known risk of prolonging the QT interval and/or causing Torsades de Pointes.
- Herbal preparations (e.g., St John's wort) are not allowed throughout the study. Subjects must discontinue herbal medications at least 7 days prior to the first dose of study treatment.
- Patients should avoid grapefruits, grapefruit juice, and Seville oranges during the study since they are known to be inhibitors of CYP3A4.
- Smoking or vaporizing of tobacco or cannabis-related products is prohibited. These products must be discontinued at least 8 days prior to the first dose of study treatment. [Note: Nicotine gum or patches are allowed, as is chewing tobacco].
- Prophylactic G-CSF may be used only in subjects with a treatment-emergent AE of febrile neutropenia while on study, or in subjects with persistent (> 5 days) Grade 4 neutropenia who are at high risk for development of febrile neutropenia.

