APPENDIX H: Drugs that Prolong the QT Interval and/or Induce Torsades de Pointes

Drugs with a Risk of Prolonging the QT Interval and/or Torsades de Pointes

Amiodarone	Clarithromycin	Haloperidol	Procainamide
Arsenic trioxide	Disopyramide	Ibutilide	Quinidine
Asetemizole	Dofetilide	Levomethadyl	Sevoflurane
Azithromycin	Domperidone	Mesoridazine	Sotalol
Bepridil	Droperidol	Methadone	Sparfloxacin
Chloroquine	Erythromycin	Moxifloxacin	Terfenadine
Chlorpromazine	Escitalopram	Pentamidine	Thioridazine
Cispride	Flecainide	Pimozone	Vandetanib
Citalopram	Halofantrine	Probucol	

Drugs with a Possible Risk of Prolonging the QT Interval and/or Torsades de Pointes

Alfuzosin	Gatifloxacin	Ofloxacin	Saquinavir
Artemether+piperaquine	Gemifloxacin	Olanzapine	Sertindole
Atazanavir Bedaquiline	Granisetron	Ondansetron	Sunitinib
Clozapine	Iloperidone	Oxytocin	Tacrolimus
Dolasetron	Indapamide	Paliperidone	Tamoxifen
Dronedarone	Isradipine	Pasireotide	Telithromycin
Eribulin	Lapatinib	Perflutren	Tizanidine
Famotidine	Levofloxacin	Lipid	Tolterodine
Felbamate	Lithium	Microspheres	Vardenafil
Fingolimod	Mirtazapine	Promethazine	Venlafaxine
Foscarnet	Moexipril/HCTZ	Quetiapine	Voriconazole
Fosphenytoin	Nicardipine	Ranolazine	Ziprasidone
	Nilotinib	Risperidone	
		Roxithromycin	

Drugs with a Conditional Risk of Prolonging the QT Interval and/or Torsades de Pointes (Should be used with Investigator discretion)

Amantadine	Diphenhydramine	Itraconazole	Ritonavir
Amisulpride	Doxepin	Ketoconazole	Sertraline
Amitriptyline	Fluconazole	Nortriptyline	Solifenacin
Chloral Hydrate	Fluoxetine	Paroxetine	Trazodone
Ciprofloxacin	Galantamine	Protriptyline	Trimethoprim-Sulfa
Clomipramine	Imipramine	Quinine	Trimipramine
Desipramine		Sulfate	

The following website was used as a guide for drugs which may prolong the QT interval:
<https://www.crediblemeds.org>. Medications listed on the website which do not appear in this appendix may be used at the discretion of the Investigator.

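### Protocol 8.1 permits quinolone prophylaxis as a class, but 7.1.4, 8.2 and Appendix H prohibit two of the seven listed quinolones, and no text says which passage governs

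*Protocol*

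**What the plan says.** Four places in the protocol bear on this.

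- **Section 8.1 (permitted medications):** "Prophylaxis with quinolone antibiotics is permitted per local standards of care". The sentence names no excluded agent and cites neither 8.2 nor Appendix H. The only reference to 8.2 comes later in the section, at the end of a different sentence: "Other medications considered necessary for subject safety and well-being may be given at the discretion of the Investigator with the exception of those listed in" (the place it then names is 8.2).
- **Section 8.2 (prohibited medications):** the list includes "Medications with a known risk of prolonging the QT interval and/or causing Torsades de Pointes", with no exemption for antibiotic prophylaxis.
- **Section 7.1.4 (precautions for pracinostat):** "Concomitant medications with a known risk of prolonging the QT interval and/or causing Torsades de Pointes are prohibited". For the lower tiers it advises caution and says that "medications with a possible or conditional risk may be used at the discretion of the Investigator", citing Appendix H.
- **Appendix H:** three lists. The first, headed "Drugs with a Risk of Prolonging the QT Interval and/or Torsades de Pointes", contains "Moxifloxacin" and "Sparfloxacin". The second and third cover possible and conditional risk, and each contains further quinolones.

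SAP 8.3 gives receipt of an excluded treatment or prohibited medication as an example of a major protocol deviation. The SAP's Per Protocol population excludes subjects with major deviations, and SAP 9.1 reports the overall response rate (ORR) for that population as well as for the ITT and efficacy evaluable populations.

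**The concern.** A site choosing an antibiotic for prophylaxis would naturally start with 8.1, which answers the question for the whole class and points nowhere else. A site that starts with 8.2 or 7.1.4 and follows the reference to Appendix H gets the opposite answer for two agents.

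Two things are at stake.

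- **Safety conduct.** QTc prolongation is a named pracinostat risk. It has an eligibility limit (4.1), its own reporting rule (6.4.1) and a rule for holding study drugs (6.5.1). Under 5.2.1, ECGs after Cycle 1 are done only when clinically indicated, so the medication rules carry more weight later in treatment. The need for prophylaxis is foreseeable, because neutropenia and febrile neutropenia of Grade 3 or above are among the events of special interest in 6.4.
- **Analysis.** The same use of moxifloxacin could be recorded as compliant under 8.1 or as prohibited medication under 8.2. The second reading can make it a major deviation and remove the subject from the Per Protocol ORR. SAP 8.3 requires such deviations to be identified before database lock, but neither document gives a rule for settling this case.

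**Working it through.** No figure in the plan is involved, so this is a text comparison plus a count.

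**Step 1: does the 8.2 exception in 8.1 reach the quinolone sentence?** The exception is attached to other medications that the Investigator considers necessary. The quinolone permission is a separate, earlier sentence whose only qualifier is local standards of care. On its wording, the exception does not reach it.

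**Step 2: is the first list in Appendix H the prohibited group?** Section 7.1.4 uses three grades (known, possible, conditional). Appendix H has three lists (risk, possible risk, conditional risk). Section 7.1.4 cites Appendix H and allows the possible and conditional grades, which leaves the first list as the known-risk group. This is an inference from the structure, because the first heading does not contain the word known.

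**Step 3: place each listed quinolone.** The appendix does not label drugs by class. Class membership is taken from the -floxacin names.

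| Appendix H list | Quinolones | Under 8.1 | Under 7.1.4 and 8.2 | Result |
|---|---|---|---|---|
| Risk (first list) | moxifloxacin, sparfloxacin | permitted | prohibited | direct conflict |
| Possible risk | gatifloxacin, gemifloxacin, levofloxacin, ofloxacin | permitted | allowed with caution, at Investigator discretion | compatible, but 8.1 omits the caution |
| Conditional risk | ciprofloxacin | permitted | allowed with caution, at Investigator discretion | compatible, but 8.1 omits the caution |

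Count: 2 + 4 + 1 = 7 listed quinolones. Direct conflict: 2 of 7. Missing caution only: 4 + 1 = 5 of 7.

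**Step 4: does any text settle the conflict?** Section 8.2 does not say that it overrides 8.1, and 8.1 does not say that it is an exception to 8.2. Section 7.1.4 repeats the prohibition without mentioning prophylaxis. No order of precedence is given.

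**Step 5: what follows in the analysis?** Status as prohibited medication feeds the major-deviation example in SAP 8.3, then Per Protocol membership, then the Per Protocol ORR in SAP 9.1. Every treated subject stays in the ITT population, so the ITT ORR does not depend on how this is resolved.

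**The case against.** The strongest reply is that the passages can be read together: quinolone prophylaxis is acceptable in principle, and agents on the prohibited list are not. Section 8.2 directly follows 8.1, its prohibition is categorical, and 7.1.4 repeats it and sets out a tiered rule. The neighbouring antiemetic sentence in 8.1 is drafted in the same way, as a class permission with no cross-reference, although Appendix H lists antiemetics too (domperidone in the first list, ondansetron and granisetron under possible risk). That suggests brevity in 8.1 and not a deliberate exemption for quinolones.

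This reading is plausible, but the documents do not state it. A specific permission placed outside the reach of the 8.2 exception can also be read as an exception to a general ban. The reply limits how serious the point is and does not remove it.

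Two objections to scope stand in full. A reader might infer that quinolones in general are both permitted and prohibited. That is not so for five of the seven, which 7.1.4 allows. A reader might also infer that the conflict will produce treatment holds or QTcF outliers. Nothing in the documents shows that either first-list agent would be used for prophylaxis at any site. Holds under 6.5.1 for QT prolongation need a sustained QTcF of at least 500 ms and/or more than 60 ms above baseline, or a new ECG finding of clinical concern, and they do not apply where there is a clear alternative cause.

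**Conclusion.** The inconsistency is real and narrow. For moxifloxacin and sparfloxacin, two of the seven quinolones in Appendix H, the protocol gives opposite instructions and does not say which governs. For the other five there is no contradiction, only the absence from 8.1 of the caution in 7.1.4.

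The point is minor in size but touches a named safety risk. It leaves unclear whether such use is a prohibited-medication deviation, and so whether a subject could leave the Per Protocol population. No sample-size figure or Stage 1 decision rule is affected. How many subjects might receive either agent is not stated and cannot be derived.

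The conclusion rests on two assumptions: that the first list in Appendix H is the known-risk group of 7.1.4 and 8.2, and that the -floxacin drugs are the quinolones meant in 8.1. Both are reasonable from the text. It does not rest on any claim that harm, holds or QTcF outliers would follow, nor on a view of which clinical rule is right.

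**What to change.** Reconcile Protocol 7.1.4, 8.1, 8.2 and Appendix H. The quinolone sentence in 8.1 should state how it relates to both the prohibited and the discretionary lists. The first heading in Appendix H should be aligned with the known-risk term in 7.1.4 and 8.2. Which agents end up permitted is a clinical decision for the sponsor.

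Once the protocol is reconciled, deviations under SAP 8.3 can be classified against a single rule, and the SAP needs no change of its own for this. The cost is one cross-reference and one heading edit in an amendment, plus notice to sites.

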8.2 Prohibited Concomitant Medications

The following treatments are prohibited while in this study:

- No other investigational therapy should be given to subjects.
- No anticancer agents should be administered to subjects. If such agents are required, the subject must first be withdrawn from the study.
- HDAC inhibitors (Zolinza [vorinostat], Istodax [romidepsin/depsipeptide]) or valproic acid (which has significant action as a HDAC inhibitor).

- Medications with a known risk of prolonging the QT interval and/or causing Torsades de Pointes.
- Herbal preparations (e.g., St John's wort) are not allowed throughout the study. Subjects must discontinue herbal medications at least 7 days prior to the first dose of study treatment.
- Patients should avoid grapefruits, grapefruit juice, and Seville oranges during the study since they are known to be inhibitors of CYP3A4.
- Smoking or vaporizing of tobacco or cannabis-related products is prohibited. These products must be discontinued at least 8 days prior to the first dose of study treatment. [Note: Nicotine gum or patches are allowed, as is chewing tobacco].
- Prophylactic G-CSF may be used only in subjects with a treatment-emergent AE of febrile neutropenia while on study, or in subjects with persistent (> 5 days) Grade 4 neutropenia who are at high risk for development of febrile neutropenia.

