Study drugs should be continued until disease progression or intolerable toxicity. It is important to note that the median time to achieving a response with azacitidine alone is 4 to 5 months. Furthermore, the median time to achieving a CR in study MEI-003 was 4 cycles. Therefore, early (< 6 months) discontinuation of study therapy for 'no response' should be avoided. The Medical Monitor should be contacted prior to discontinuing study drugs in a subject to discuss the rationale for discontinuation.

After discontinuing study drugs, subjects will be followed every 3 months (± 1 month) until death or study termination to collect information on disease status (i.e., improvement of disease response or disease progression), start of non-protocol therapies (e.g., stem cell transplant or an MDS-directed therapy) and survival.

The primary study analysis will be performed approximately 12 months after the last subject is enrolled in the study. The study duration is anticipated to be approximately 36 months: 24 months for enrollment and 12 months of follow-up until the primary analysis. At the completion of the primary analysis, the Sponsor will decide whether to terminate the study or continue study drug dosing in ongoing subjects.

STUDY DRUGS, DOSES, AND MODES OF ADMINISTRATION

Pracinostat: 45 mg administered orally 3 days each week (e.g., Monday, Wednesday, Friday) for 3 consecutive weeks, followed by 1 week of rest, in 28-day cycles.

In later cycles (i.e., after Cycle 4), 45 mg pracinostat can be reduced to orally 3 days each week \times 2 weeks (instead of 3 weeks) or dose interruption is allowed to manage toxicity such as fatigue, gastrointestinal toxicity, or myelosuppression.

Azacitidine: All subjects will receive a standard regimen of azacitidine at 75 mg/m² for 7 days of each 28-day cycle. Administration will occur by subcutaneous (SC) injection, or intravenous (IV) infusion if SC injections are not tolerated, on one of two schedules:

- Schedule 1 – daily therapy on Days 1 through 7
- Schedule 2 – 5-2-2 schedule in which subjects receive azacitidine for 5 consecutive days (Days 1 through 5) with rest on Days 6 and 7, and resume azacitidine dosing the first two days of the next week (Days 8 and 9) of each 28-day cycle.

Subjects may be treated on either azacitidine schedule, however the preference is to have subjects stay on the same schedule during their participation in the study.

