4.3 Discontinuation from Study Treatment

The Medical Monitor should be contacted prior to discontinuation of study treatment.

Subjects will be discontinued from study treatment for any of the following reasons:

- Documented disease progression or relapse after CR/PR by the International Working Group (IWG) criteria (see [Section 5.2.4](#)). Because subjects with MDS receiving HMAs may require more than 6 cycles of therapy to achieve a response (median 4 to 5 cycles), discontinuation due to “lack of response” in the first 6 cycles of therapy must be avoided.
- Decision to proceed to intensive therapy and stem cell transplant.
- Irreversible or intolerable toxicity or abnormal and clinically significant laboratory values thought to be related to drug toxicity and not manageable by supportive approaches and/or study drug dose reduction or interruption.
- Pregnancy.
- Subject request to withdraw from treatment or from the study.
- Conditions requiring therapeutic intervention not permitted by the protocol.
- Lost to follow-up.
- Non-compliance with study treatment or study-related assessments that compromise the proper evaluation of the patient’s safety.
- Early study termination by the Sponsor, the Sponsor’s designee, or regulatory authorities.

After discontinuation from protocol treatment, subjects must be followed for AEs for 30 calendar days after their last dose of study medication. All new AEs occurring during this period must be reported and followed until resolution, unless, in the opinion of the Investigator, these AEs are not likely to improve because of the underlying disease.

All subjects who have Grade 3 or 4 laboratory abnormalities (National Cancer Institute Common Terminology Criteria for Adverse Events [NCI CTCAE] v4.03) at the time of discontinuation must be followed until the laboratory values have returned to Grade 1 or 2, unless it is, in the opinion of the Investigator, not likely that these values will improve.

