5.4 Follow-up

After subjects discontinue study drug, they will be followed every 3 months (\pm 1 month) until death or study termination to collect information on progression, any new treatments, and survival (e.g., date and cause of death). With suspicion of disease progression, a CBC (including 3-part differential, platelets, and blasts) may be performed (optional). Subjects may be contacted during outpatient visits or by telephone.

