APPENDIX A Schedule of Events

Assessments/Procedures	Screening ^a		Treatment Cycles (28 days -4 to + 7 days) ^b										End of Treatment visit ^q	Follow-up ^r
	Day -14 to 0	Day 1	Day 2	Day 3	Day 4	Day 5	Day 6	Day 7	Day 8	Day 9	Day 15 ^p	Day 22 ^p		
Obtain Informed Consent ^c	X													
Determine eligibility ^d	X													
Medical history, including recent smoking history	X													
Transfusion history for 8 weeks prior to first study drug administration	X	X												
Physical examination	X	X												
Vital signs ^e	X	X									X	X		
Smoking assessment ^f		X									X	X	X	
ECOG Performance Status	X	X											X	
Baseline signs and symptoms	X													
AE/toxicity assessment ^f	X	X	X	X	X	X	X ⁿ	X ⁿ	X ^o	X ^o	X	X	X	
Concomitant medication review	X	X											X	
12-Lead ECG in triplicate ^g	X	X												
CBC ⁱ	X	X									X	X	X	
Serum Chemistry ^h	X	X									X	X	X	
Serum pregnancy test (if applicable) ^j	X													
Bone marrow aspiration and biopsy ^k	X												X	
Assess study medication compliance ^l		X											X	
New Treatments and Survival														X
Dispense/administer pracinostat ^l		X												
--Azacitidine Administration (1-7) ^{m,n}		X	X	X	X	X	X	X						
--Azacitidine Administration (5-2-2) ^{m,o}		X	X	X	X	X	X			X	X			

Abbreviations: AE = adverse events; CBC = complete blood count; ECG = electrocardiogram; ECOG = Eastern Cooperative Oncology Group.

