- Leukemic transformation rate: leukemic transformation at landmark time points of 6, 12, 18, and 24 months.
- Event-free survival (EFS), defined as the time from the first day of study drug administration (Day 1) to disease progression, relapse or death from any cause. Subjects who are alive and free from disease progression will be censored at the date of last disease assessment .
- Progression-free survival (PFS): time from the first day of study drug administration (day 1) to progression per IWG criteria, or death on study. Subjects who are alive and free from disease progression will be censored at the date of last disease assessment.
- Overall survival (OS): time from the first day of study drug administration (day 1) to death from any cause on study. Subjects who are alive will be censored at the date of last visit or contact with the investigator.
- Time to Stem Cell Transplant (SCT): time from the first day of study drug administration (day 1) to SCT, for subjects with SCT. If no SCT date can be confirmed, SCT date will be imputed as study drug discontinuation day.

For each of DOR, EFS, PFS and OS, in the sensitivity analyses, subjects with no events who stopped treatment and received SCT will be censored at the SCT day (either confirmed SCT day, or study drug treatment discontinuation day, if no SCT date can be confirmed) even if there were events which occurred after the SCT date.

- For both stages, the rate of treatment discontinuation in the first 3 cycles of therapy due to possibly safety-related reasons will be used as a secondary endpoint to evaluate the safety and tolerability. Progressive disease and transplant are reasons to discontinuation related to efficacy, therefore these events will be excluded from the analysis. All the other reasons for treatment discontinuation will be considered as possibly safety-related, therefore will be included in the analysis as events.

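### Section 8.2 requires withdrawal from the study before another anticancer agent, which contradicts Sections 4.3 and 5.4 and may informatively censor overall survival at sites that apply it literally

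*Protocol*

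**What the plan says.** - **Protocol 8.2** bars other anticancer agents while a subject is in the study and adds: "If such agents are required, the subject must first be withdrawn from the study".
- **Protocol 4.3** gives the reasons for discontinuing study treatment. One is "Conditions requiring therapeutic intervention not permitted by the protocol". Another is "Subject request to withdraw from treatment or from the study", so the list itself treats the two kinds of withdrawal as different things.
- **Protocol 5.4** follows subjects who have stopped study drug every 3 months (± 1 month) "until death or study termination to collect information on progression, any new treatments, and survival". The synopsis and Section 3 describe the same contact as collecting disease status, "start of non-protocol therapies (e.g., stem cell transplant or an MDS-directed therapy) and survival". In Appendix A the item marked in the follow-up column is "New Treatments and Survival".
- **OS.** SAP 2.3.2 defines it as "time from the first day of study drug administration (day 1) to death from any cause on study". Protocol 9.3.1 also counts death on study. The SAP censors living subjects at the last visit or contact with the investigator. Censoring at stem cell transplant is a sensitivity analysis only.
- **Leukemic transformation** is reported at 6, 12, 18 and 24 months. Neither document says how a subject who has left before a landmark is scored.

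**The concern.** A subject who has been withdrawn from the study has no protocol-defined contact at which a new treatment or a later death would be recorded. Section 8.2 taken literally therefore removes the information that Section 5.4 is written to collect. Sites following one section would produce different survival follow-up from sites following the other.

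The loss would not be random. Subjects who need another anticancer agent are mostly those whose disease is no longer controlled, and the protocol's background puts median survival after failure of a hypomethylating agent at under one year. Censoring them when they switch breaks the Kaplan-Meier assumption that censored subjects have the same prospects as those still followed. The OS curve would be pushed upwards. There is no concurrent control arm, so OS can only be read against outside data, and nothing within the trial would reveal the shift.

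**Working it through.** **1. The passages side by side**

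| Question | 8.2 | 4.3 | 3, 5.4, Appendix A |
|---|---|---|---|
| What ends when non-permitted therapy is needed? | The study | Study treatment | Study drug only |
| Is the new therapy recorded? | Not if withdrawal comes first | Not addressed | Yes |
| Is survival recorded afterwards? | Not stated | Not addressed | Yes, to death or study termination |

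No passage says that a subject withdrawn under 8.2 stays in follow-up. The rows cannot all be met if 8.2 is taken at its word.

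**2. Which endpoints are exposed**

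- *OS*: exposed. A death after study withdrawal can be read as not on study, and the subject is then censored at last contact.
- *PFS and duration of response*: little affected for a switcher who has already progressed, because the event has occurred.
- *ORR*: little affected.
- *Transformation*: not established. After treatment, 5.4 relies on visits or telephone contact and an optional blood count, and there is no landmark denominator rule. The endpoint is weak after study drug stops whatever 8.2 means, and no calculation was made for it.

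**3. Possible size for OS**

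The documents give no target precision or event count for OS, so there is no plan figure to reproduce. The following is an illustration.

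Inputs from the documents:
- median time to first event 9 months (MEI-003 event-free survival), so the monthly hazard is ln 2 / 9 = 0.077;
- 24 months of accrual plus 12 months, so administrative censoring C is uniform on 12 to 36 months;
- median survival after hypomethylating-agent failure below 12 months.

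Assumptions:
- 70% or 80% of first events are progression and the rest are death;
- post-progression median survival is 6 to 10 months, the same for switchers and non-switchers;
- 25%, 50% or 75% of progressors are lost one month after progression.

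Model: T1 is the time to first event and T2 the exponential post-progression survival. Death time is D = T1 if the first event is death, otherwise D = T1 + T2. With full follow-up, observed time is min(D, C). For a lost switcher, C is replaced by min(C, T1 + 1). Kaplan-Meier medians come from 400,000 simulated subjects per scenario.

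| Progression share | Post-progression median (months) | Full follow-up | 25% lost | 50% lost | 75% lost |
|---|---|---|---|---|---|
| 80% | 6 | 16.2 | 17.4 | 19.4 | 22.9 |
| 80% | 8 | 18.1 | 19.4 | 21.3 | 24.8 |
| 70% | 6 | 15.3 | 16.3 | 17.7 | 20.0 |

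At 50% lost the excess in these rows is 19.4 − 16.2 = 3.2, 21.3 − 18.1 = 3.2 and 17.7 − 15.3 = 2.4 months. Over the full 6-to-10-month range it is about 2.2 to 3.3 months. In the first row, observed deaths among 60 subjects fall from about 40 to 33, 27 and 21.

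*Sensitivity to timing.* If switchers are lost at progression itself, with 20% or 40% of first events being death and a post-progression median of 6, 9 or 12 months, the excess at 50% lost runs from 19.3 − 17.9 = 1.4 to 20.3 − 16.2 = 4.1 months. Over all shares it runs from 18.5 − 17.9 = 0.6 to 25.2 − 16.2 = 9.0 months.

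*Partial literal reading.* The share lost is the switching share times the share of switchers at sites that apply 8.2 literally. If half of progressors switch and half of those are at such sites, 0.5 × 0.5 = 25% are lost and the 25% column applies. If all sites follow 5.4, none are lost and the excess is zero.

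**The case against.** The best defence is that the documents as a whole show follow-up was meant to continue. Four passages support this.

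- Section 4.3 places therapy not permitted by the protocol among the reasons to stop *treatment*.
- Sections 3 and 5.4 and Appendix A collect new therapies. They could never be observed if 8.2 ended participation first.
- A subject who progresses stops treatment under the first reason in 4.3 and passes into 5.4 follow-up without needing 8.2.
- The SAP censors at transplant only as a sensitivity analysis, so its main OS analysis expects events after subsequent therapy.

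The protocol also uses *study* loosely for treatment. Section 5.3 speaks of discontinuing the study when it describes the end-of-treatment visit, and Appendix A calls the same evaluations End of Study. Section 6.4.2 discontinues pregnant subjects from the study, while 4.3 lists pregnancy under study treatment. Section 8 concerns concomitant medication, so 8.2 can be read as barring concurrent agents during treatment. *On study* is undefined, and a death during protocol follow-up may well qualify.

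Most of this stands. A reader might infer that the plan loses every switcher from OS and transformation, or that a subject progressing at month 8 is censored for OS at about month 9. The documents do not support either inference: the loss arises only where a site sets 8.2 above 5.4.

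The defence does not remove the contradiction. Section 8.2 is a mandatory instruction, its prohibitions run for as long as the subject is in the study, and no text says follow-up survives the withdrawal. Compliance with a stated rule should not depend on a site inferring that it means something else.

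**Conclusion.** The wording conflict between 8.2 and Sections 3, 4.3, 5.4 and Appendix A is certain. The bias is conditional: OS may be informatively censored, in the favourable direction, to the extent that sites follow 8.2 literally.

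The size cannot be fixed from the documents. It is zero if 5.4 governs. It is about 2 to 3 months of median OS if 50% of progressors are lost one month after progression. For scale only, the MEI-003 median OS figures were 16 and 19 months, a 3-month difference, with a hazard ratio interval of 0.65 to 2.23. The switching share, the degree of literal compliance, the exponential times and the equal prognosis of switchers and non-switchers are all assumptions.

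It would go too far to say that the transformation rates are biased downwards. Without a landmark rule, neither the direction nor the size is established. The point concerns secondary, descriptive endpoints and leaves the primary ORR largely untouched. It should still be corrected, because deaths that go unrecorded may not be recoverable later.

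**What to change.** 1. **Protocol 8.2, 4.3 and 5.4.** Reconcile them, leaving the prohibition on other anticancer agents unchanged, so that the documents state that a subject who starts another anticancer agent remains in Section 5.4 follow-up for survival and transformation unless consent to follow-up is withdrawn.
2. **Protocol 9.3.1 and SAP 2.3.2.** Define the OS event as death from any cause up to the data cut-off, in place of death on study. Carry the same wording into SAP Section 13, which restates the OS definition.

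The cost is a few sentences across the two documents. No visits are added, because the 3-monthly contact is already planned. When study treatment stops and which agents are barred remain as the sponsor has set them.
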